### **Recruitment and Data Collection prior to Test date:**

Case:

- At the end of their appointment with one of the endometriosis specialists at the BC Women's Health Centre for Pelvic Pain and Endometriosis, the physician will ask the patient if they are interested in learning more about this research study (if the physician deems them acceptable to be included based on screening of inclusion and exclusion criteria). The physician will provide the patient a copy of the consent form to read at home and will ask the patient if [name] or her delegate can call them in the next couple of days. Physicians will emphasize that participation is optional and does not influence their health care.

- A poster introducing the study will also be available in the clinic waiting rooms.
- Potential participants will be encouraged, if they feel comfortable doing so, to discuss the consent form with family, friends, and/or their physician. The potential case participants will be given a minimum of 24 hours to review the consent form before being contacted by [name] or her delegate.
- [name] will collect the physician forms and will confirm that the interested potential case participants consented to the data registry. [name] will only give [name] the contact information of the potential case participants that consented to the data registry. During the first phone call, [name] or her delegate will ask if the potential case participant is interested in participating in the study, and will explain the study and consent process, if they wish. During this phone conversation, [name] will remind the potential case participant that they have consented to the data registry, and consent to this study allows us access to analyze their data registry data. Verbal consent will be given if the potential case participant would like to participate, and a test appointment will be booked. [name] or her delegate will log the participant into the test computer during the test day so that they can complete the test day questionnaire online.
- Case participants will sign the consent form in-person at the beginning of the test day appointment.
- Note that the case participants do not need to complete the Data Registry questionnaire again, since we will be linking to their previously completed Data Registry questionnaires done before their physician appointment.

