- Participants will be instructed not to take analgesics within 24 hours before the scheduled test, nor to take opioids within 2 weeks before the scheduled test, nor to consume alcohol within 24 hours prior to scheduled test time. The participants will also be told to wear comfortable clothing with easy access to their shoulder for the scheduled appointment.

Control:

- Recruitment of the control group will be done by poster advertisement at the BC Women's Hospital. If they are interested in the study, potential participants will be asked to contact [name] (contact information on poster) to learn more about the study.
- In addition to a poster advertisement, the research assistant will circulate an invitation (via. email/social media) to an in-person information session open to all potential control participants who may be interested in the study.
- In-person information sessions and poster advertisement may also be done at the BC Children's Hospital, the BC Children's Hospital Research Institute (BCCHRI), and the University of British Columbia.
- An in-person information session includes: a short presentation about the research study and what is required of the control participants, and contact information will be left for the potential control participants if they would like more information/if they would like to participate.
- Recruitment of control participants may also be done through institutional research newsletters.

- [name] or her delegate will mention to participants in the study that their friends and family are welcome to contact us if they would like to participate, and will provide the participant a copy of the poster. This will happen at the final interaction between the participant and the research so they do not feel pressure.
- In addition, we will recruit via electronic forms of communication (e.g. institutional listservs (CRC net for the BC Children's Hospital Research Institution) or research/student groups).

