- [name] or her delegate will provide the potential control participant with a copy of the consent form (in person or by email). Each potential control participant will be advised to carefully read the consent form, and to contact [name] with any questions about the information contained in the consent form. Potential participants will be encouraged, if they feel comfortable doing so, to discuss the consent form with family, friends, and/or their physician. The interested control participants will give [name] or her delegate their contact information via in person or email. They will be given a minimum of 24 hours to review the consent form before being contacted by [name] or her delegate who will ask if they would like to take part in the study.
- If the control participant expresses interest in the study after reading the consent form, [name] or her delegate will send them a link to access the REDCap screening questions indicating sexual and non-sexual pains, age, and history of fibromyalgia (see attachment). Each control subject will be assigned a de-identified unique study ID.
- Criteria will be assessed by screening questions. If the participants are eligible based on the screening questions (18 years or older, pain scores less than 4/10, and no fibromyalgia) then they will be asked if they would like to consent to the study (online consent). This online consent allows access to the data from the screening questions. If they are not eligible, or do not consent to the study their screening questions will not be analyzed. If the control participant consents online they will be asked to complete additional questions on REDCap (height, weight, etc. See attached).
- [name] will receive an email from REDCap once the control participant has consented online, and will contact the participant to book a test day appointment.
- If the control participant had not completed the pre-test questionnaire after one week, they will be sent an email reminder.
- On the test day, the consent participants will sign the same consent form in-person to consent to the testing procedures.
- Participants will be instructed not to take analgesics within 24 hours before the scheduled test, nor to take opioids within 2 weeks before the scheduled test, nor to consume alcohol within 24 hours prior to scheduled test time. The participants will also be told to wear comfortable clothing with easy access to their shoulder for the scheduled appointment.

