#### Data Linking:

The Data Registry for Chronic Pelvic Pain and Endometriosis (H16-00264) collects a wide range of data from all consenting patients of the BC Women's Centre for Pelvic Pain and Endometriosis including those who undergo surgery at the clinic. Case participants in this study (Endometriosis deep dyspareunia and central sensitization) are therefore also listed in the Data Registry (they consent to both). This will allow for direct matching. A data access request will be sent to the research coordinator ([name]) to collect the case participant data from the Data Registry. The information provided to the Data Registry research coordinator for data linking includes: unique study ID, MRN, PHN, first and last name, and date of initial visit to BC Women's Health Centre. All the data from the Data Registry is being linked. This data will be placed in an encrypted excel file on the O: drive. The research coordinator will pull the appropriate information and replace the participants Data Registry REDCap ID with the unique study ID for this study and place the file back on the O: drive, where [name] or her delegate will have access to it. Data for both studies are kept on the BC Women's secure O: drive in separate password protected folders with restricted access to study team members; therefore the data transfer can be undertaken within the PHSA secure network.

Once data linkage is complete the linking spreadsheet sent to the Data Registry research coordinator will be permanently deleted as per UBC policy 85.

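### The two-week opioid stop before sensory testing comes with no described check for women who take opioids regularly

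*Combined protocol and SAP*

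**What the plan says.** The instruction appears twice under Recruitment and Data Collection prior to Test date, once for cases and once for controls, in the same terms. The case list tells participants to take no analgesics for 24 hours, "nor to take opioids within 2 weeks before the scheduled test"; in the control list they are likewise "instructed not to take analgesics within 24 hours before the scheduled test, nor to take opioids within 2 weeks before the scheduled test". Neither list adds an exception, a taper or a rule for a woman who cannot stop.

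Inclusion Criteria and Exclusion Criteria do not mention opioids or analgesics, so regular users are eligible in both groups.

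For cases, the clinic specialist decides whether to raise the study "based on screening of inclusion and exclusion criteria". A research call follows after at least a day: "Verbal consent will be given if the potential case participant would like to participate, and a test appointment will be booked". The consent form is signed at the test visit. For controls, the eligibility items named for the online screen are "18 years or older, pain scores less than 4/10, and no fibromyalgia"; online consent and a booking contact follow.

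The risk paragraph under Ethical Considerations covers the pressure test, the personal questions and accidental data release. It does not mention going without opioids.

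**The concern.** Cases come from a pelvic pain and endometriosis clinic, and the ethics section itself allows for a history of chronic pain. It would not be surprising if some took opioids on prescription. For such a woman, a two-week stop is a change in treatment made for research purposes. Followed literally, the rule could lead her to stop abruptly at home, with no clinician having considered whether that is safe. The plan states that she gains no direct health benefit from taking part. She may decline, or raise it with her doctor, but the visible text leaves that to her.

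What is at stake is participant safety. No effect on the primary Spearman correlation or on the sample size is claimed.

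**Working it through.** There is no figure in the plan to reproduce. The check is whether any visible step stands between a regular opioid user and the instruction.

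**Timing.** Call the test day 0. Opioids are to be withheld from day −14 to day 0. To be followed, the instruction must reach the participant by day −14, so a useful check has to come at or before booking. The plan sets no minimum interval between booking and test.

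**Each step that might serve as the check:**

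| Step | Timing | What the visible text says | Does it close the gap? |
|---|---|---|---|
| Specialist's screening (cases) | Before booking | Screening is against the eligibility criteria, which do not mention opioids | No. The specialist may know her medication, but no use of that knowledge is described |
| Talking it over | Before booking | Participants are encouraged "to discuss the consent form with family, friends, and/or their physician" if comfortable doing so | No. It is voluntary and concerns the consent form |
| Booking call (cases) | Before booking | Study and consent process explained, verbal consent taken, test booked | No. No medication question is described |
| Screening questions (controls) | Before booking | Age, pain scores and fibromyalgia are named | No, as far as can be seen. The attached lists are not available |
| Data Registry (cases) | Before the clinic appointment | Cases have "previously completed Data Registry questionnaires done before their physician appointment", and the registry "collects a wide range of data from all consenting patients" | No. It may hold medication data, but no look-up before testing is described |
| Test-day questionnaire | Day 0 | Asks whether medication has changed since the last clinic visit | No. It comes when the 14 days are over and asks about change, not current use |
| Nurse triage | Once a reaction has occurred | The clinic nurse triages adverse reactions, with a physician if required | No. It responds to harm and does not prevent the stop |

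**Consent sequence.** Cases agree by phone and sign on day 0, so their withholding period falls before signed consent. Controls consent online before booking and sign on day 0. No physician contact is described for controls beyond the voluntary discussion.

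**Size.** The documents do not give the number of regular opioid users. As a bare assumption with no source, at 0%, 5% or 10% of the 126 planned cases:

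- 126 × 0 = 0
- 126 × 0.05 = 6.3, about 6
- 126 × 0.10 = 12.6, about 13

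The range includes zero, and the conclusion does not depend on where in it the truth lies.

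**The case against.** The strongest reply is that much of the relevant material is out of sight. The consent form, the forms completed by the clinic physicians, the control question lists and the flow charts in Appendices A and B are all places where a medication check could sit. This stands. A reader might infer that the study has no check at all, or that participants are not warned. The documents do not support that; they show only that the readable protocol describes no check and that its risk paragraph omits this risk.

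A second reply is that the harm needs a chain of events. A regular user must enrol, stop suddenly, and consult neither the specialist who has just seen her nor her own prescriber. The rule can also be read as a condition that she cannot meet, so that she would decline. This is fair, and it limits the likely number affected. It does not remove the point, because the text addresses participants and does not say that someone who cannot stop should decline.

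A third reply concerns scale. The instruction reaches all 126 + 50 = 176 planned participants, and a reader might take that as the number at risk. It is not, since only regular opioid users are exposed. Controls are screened for low pain scores, so such use among them is plausibly rare.

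Finally, a reader might extend the point to the 24-hour analgesic rule and ask for clearance there too. The documents give no ground for expecting harm from a one-day pause in a non-opioid analgesic. In a pain clinic, such a requirement could delay many more women.

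**Conclusion.** The concern holds in a limited form. As visible, the protocol gives an unqualified two-week opioid stop, leaves regular users eligible, and describes no check of current use or prescriber's agreement before the stop begins. A regular user following it could stop abruptly without medical review. This is more than missing detail, because the exposure comes from carrying out a stated rule as written.

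The number of women concerned is unknown and may be none. The conclusion rests on two assumptions: that the unseen forms do not already contain such a check, and that at least one regular user might enrol and comply. It is a cheap safety improvement. The omission from the ethics section's risk paragraph is a documentation matter and would not justify an amendment by itself.

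**What to change.** Before booking, ask: *Do you currently take opioids regularly?* For cases, ask at the physician's screening or, at the latest, in the booking call. For controls, ask in the online screening questions or at the booking contact.

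If the answer is yes, tell her not to stop for the study unless the clinic physician (cases) or her own prescriber (controls) agrees, and do not book the test until that is settled. If an unseen form already asks this, the protocol need only say so and tie the answer to booking.

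Add the risk of withholding opioids to the risk paragraph under Ethical Considerations. Leave the 24-hour rule for non-opioid analgesics unchanged. The clinical content of the opioid rule is for the clinic physicians.

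The cost is one question at an existing contact and a sentence or two of text, through an ethics amendment. The downside is that a few regular opioid users may be delayed or not tested.

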#### Procedures for Data Collection (on Test day)

#### **Questionnaire:**

#### Case and Control:

- Data will be collected during a scheduled appointment with [name] or her delegate. The research visit will take approximately one hour of the participant's time (not including travel time to and from the site). The visit will take place in a BC Women's Health Centre private room (4th floor of the Shaughnessy building at the BC Women's Hospital). Data collected will include an online questionnaire containing: today's date, score of sexual and non-sexual pains, first day of last menstrual period, any changes in medication since their last visit to BC Women's Health Centre, current hormonal suppression, date of last physician appointment, menstrual cycle data, last time they have had sexual intercourse and how many times have they had sexual intercourse in the last one month. The pelvic pain questions asked on this online questionnaire are modified from the Brief Pain Inventory Short Form. This questionnaire will be filled out on REDCap online using a desktop computer in the room.
- The testing room will be maintained at a temperature between 20 and 25 degrees Celsius, with no fans or open windows (may use a white noise machine), and no stressful stimuli (e.g., no loud noises or blinking lights).
- As the participant completes the online questionnaire, [name] or her delegate will set up the Algometer and calibrate the force sensing resistor (FSR). [name] or her delegate will answer any questions.

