*“This instrument is called the Electronic Thimble Algometer and will be used today to measure your pain pressure threshold. The pain pressure threshold is when the sensation of pressure changes to the first sensation of pain. During this test I will place this part of the instrument, called the force sensing resistor, on the end of my index finger and will apply a constant pressure to your right shoulder, left shoulder, right first dorsal interosseous muscle and your left first dorsal interosseous muscle. The pain-pressure threshold measurement from these four sites will be duplicated. The order of the test sites will be determined randomly. I will constantly apply pressure to the test site until you click on the mouse indicating that the sensation of pressure has changed to the sensation of pain. Please click the mouse at your first sensation of pain. There will be a thirty second break between each test site, and then a two minute break before duplicating the test. You will hear the prompt for the next test site after each of the breaks. If at any time you are no longer comfortable or change your mind about participating, please let me know. I will then stop the testing immediately. Do you have any questions before we begin?”*

This script will be read to each participant before the test begins. Any questions or concerns they have will be answered to the best of the investigators ability and/or addressed before they willingly partake in this test.

- The participants will be blinded to the computer screen (where the PPT data is shown) to ensure they are not influenced by the data during the QST
- The observation made by this QST is that a lower PPT is suggestive of increased central sensitization.
- After testing the individual will remain in the test room until she feels ready to leave.

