#### DATA ANALYSIS

---

The data collected from the 30 case participants was used to execute a power analysis to determine the total sample size required for the study. With power=0.80 and  $\alpha=0.05$  two tailed, a sample size of 126 case participants was needed.

For the cases, statistical analysis following collection of the data will be done using a Spearman Correlation determine if there is significant association between PPT and the primary outcome (deep dyspareunia) and secondary outcomes (e.g. non-sexual pain). Mann-Whitney association may be done for the bladder and pelvic floor variables to determine if they are significantly associated with PPT. Multiple Variable Regression may be done using variables significantly associated to determine if they are independently associated, independent of possible confounders. Comparison of PPT between cases and controls will also be done, but the main reason for the controls is for troubleshooting of the QST.

---

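### Pressure-pain threshold is pressed by hand and a delegate may do the testing, but no tester code is described or used in the analysis; adding one is a cheap improvement

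*Combined protocol and SAP*

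**What the plan says.** All references are to the combined protocol and SAP.

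- **Role of PPT.** The Design section names central sensitization, measured by PPT, as the main independent variable.
- **Who tests.** Procedures for Data Collection (on Test day) states: "Data will be collected during a scheduled appointment with [name] or her delegate". The same person sets up the algometer and calibrates the sensor. The number of delegates and their share of visits are not given.
- **How pressure is applied.** In the Quantitative Sensory Testing script the tester tells the woman: "I will place this part of the instrument, called the force sensing resistor, on the end of my index finger". The tester presses until she clicks the mouse. No rate of force increase, tester training or between-tester check is described.
- **What is kept.** The Quantitative Sensory Testing section and the privacy text under Ethical Considerations describe a paper sheet with the study ID and the PPT values, later entered in an encrypted file. Tester is not among the items described. Paper data are to be shredded under hospital policy, and the test laptop keeps no participant data.
- **Analysis.** Data Analysis plans a "Spearman Correlation determine if there is significant association between PPT and the primary outcome", within cases and without adjustment. It adds "Multiple Variable Regression may be done using variables significantly associated"; the confounders are not named and tester is not mentioned. A case-control comparison of PPT is also planned.
- **Sample size.** "The data collected from the 30 case participants was used to execute a power analysis", and at power 0.80 and alpha 0.05, "two tailed, a sample size of 126 case participants was needed". The correlation assumed is not stated.

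**The concern.** A threshold read from a hand-pressed sensor depends on the woman and also on how fast and at what angle the tester presses. When values from several testers are ranked together, part of the ranking reflects technique.

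The safeguards in the plan do not address this. Calibration standardises the sensor. The script standardises what is said. Random site order balances sites. Averaging eight readings reduces within-session error, but the script has one speaker doing the whole test, so a tester effect would be common to all eight readings and would survive the averaging.

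Two things are at stake. Tester variation unrelated to pain weakens the primary correlation. Tester use that follows severity, or calendar time while the case mix drifts, could move that correlation in either direction. The case-control comparison, which carries the secondary hypothesis, would shift if the groups were tested by different mixes of people. Without a tester code the analyst can neither check nor correct for any of this, and once the paper sheets are destroyed the information may not be recoverable.

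**Working it through.** **Inputs from Data Analysis:** 126 cases, power 0.80, two-sided alpha 0.05, Spearman correlation, 30 cases as the source of the power analysis. **Assumed, because the documents give no value:** *s*, the share of observed PPT variance due to testers that was absent from the planning correlation.

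**1. The plan's own figure.** The effect size is not stated, so 126 can only be solved backwards. By Fisher z:

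r = tanh((1.960 + 0.842)/√(126 − 3)) = tanh(2.802/11.09) = 0.247.

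With a variance factor of 1.06 for Spearman, r = 0.254. So 126 is plausible for a correlation of about 0.25, but this does not confirm it: a two-group comparison at a standardised difference of 0.5 also gives 63 + 63 = 126.

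**2. Attenuation.** If tester is unrelated to deep dyspareunia, r_obs = r·√(1 − s), and power = Φ(atanh(r_obs)·√123 − 1.960). For s = 10%: r_obs = 0.2474 × √0.90 = 0.2347; atanh = 0.239; 0.239 × 11.09 − 1.960 = 0.69; power = 0.756.

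| s (assumed) | r_obs | Power at 126 | Cases needed for 80% |
|---|---|---|---|
| 0% | 0.247 | 80.0% | 126 |
| 2% | 0.245 | 79.2% | 129 |
| 5% | 0.241 | 77.9% | 133 |
| 10% | 0.235 | 75.6% | 141 |
| 20% | 0.221 | 70.4% | 159 |

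**3. What a share means.** For two testers whose means differ by d standard deviations, with fraction p of women seen by one of them, s = d²p(1 − p)/(1 + d²p(1 − p)). With equal use and d = 1, s = 0.25/1.25 = 20%. With equal use and d = 0.5, s = 0.0625/1.0625 = 5.9%. With an 80/20 split, a share of 20% needs d = 1.25, since 1.5625 × 0.16 = 0.25.

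**4. Check by simulation.** Spearman tests, n = 126, two testers, underlying r = 0.254, tester unrelated to outcome, 8,000 runs per cell (simulation error about √(0.78 × 0.22/8000) = 0.5 points). Adjusted means ranks corrected for tester.

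| d | Equal use, unadjusted | Equal use, adjusted | 80/20, unadjusted | 80/20, adjusted |
|---|---|---|---|---|
| 0 | 78.3% | 77.4% | 78.2% | 78.9% |
| 0.3 | 77.4% | 77.9% | 77.8% | 78.7% |
| 0.5 | 76.3% | 77.7% | 76.7% | 77.5% |
| 0.8 | 72.1% | 77.5% | 74.6% | 78.1% |
| 1.0 | 68.0% | 77.7% | 71.9% | 78.2% |

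The baseline is 78% and not 80% because the formula is approximate for Spearman. Adjustment holds power at about 77-79% whatever the shift, and costs almost nothing when there is no tester effect.

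**5. Case-control shift.** Bias = d × (difference between groups in the fraction seen by one tester). As an assumed example, d = 0.5 with fractions of 0.5 and 0.2 gives 0.5 × 0.3 = 0.15 standard deviations.

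**The case against.** The strongest objection concerns power. The sample size came from 30 cases of this same study. If the same mix of testers examined those women, tester noise is already in the planning correlation, and deducting it again counts it twice. That stands. A reader might infer that the stated 80% is not delivered, but the documents do not support this: they do not say who tested the 30, or that tester variation grew afterwards.

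A reader might also infer that tester is not recorded at all. The PPT sheet and the questionnaire attachments are not in the text, and the list in the test-day section is the participant's questionnaire, not a full inventory of staff records. The supportable wording is that tester is not described as recorded.

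Nor do the documents show testers rotating. The delegate wording recurs for phone calls and reminders, and the Quantitative Sensory Testing section speaks of the investigator in the singular. One person testing nearly everyone fits the text equally well.

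Finally, the 20% share needs a gap of about one standard deviation between two equally used testers, which is large after calibration and a fixed script, and the case-control comparison is expressly subordinate. Both are fair, and they limit the size of the point. They do not remove it: the plan permits more than one tester and provides no means of checking for a tester effect.

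**Conclusion.** The point holds as a conditional one: a hand-applied main variable, more than one permitted tester, and no tester identity in the described record or in the analysis. If only one person tests, nothing is lost. If several do, the effect on the primary correlation is about 2-4 points of power at assumed shares of 5-10% and about 10 points at 20%. These losses apply to the stated 80% only in so far as tester variation exceeds what the 30 cases already contained. They also rest on a planning correlation of about 0.25, inferred from 126, and on tester being unrelated to severity; where it is related, the result is bias of unknown direction. The documents do not establish a shortfall in power. Even if the pilot already contained tester noise, adjustment could recover precision and would allow the bias check. **Label: cheap improvement.**

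**What to change.** 1. Add a tester code to every PPT sheet and to the encrypted data file. For women already tested, reconstruct it where possible, for example from appointment records if these exist, before any paper is destroyed.
2. In Data Analysis, prespecify a partial Spearman correlation of PPT with deep dyspareunia adjusted for tester, at minimum as a sensitivity analysis beside the unadjusted one. Adjusting the pooled ranks is preferable to ranking within tester, which wastes information if a delegate saw only a few women.
3. Include tester in the case-control comparison of PPT.
4. Report the number of testers and how many cases and controls each examined. If there was only one, that settles the question.

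Cost: one field per visit, a sentence or two in Data Analysis, and 1-2 degrees of freedom with two or three testers. The main drawback is that codes may be missing for the first 30 cases, which are 30/126 = 24% of the planned cases. In that event, report how many codes are missing and run the adjusted analysis both with those women as a separate category and without them.
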